# Advanced Germline BRCA-mutated Ovarian Cancer After 3 or More Lines of Chemotherapy

#### Pooled Data

The safety of Olaparib was investigated in 223 patients (pooled from 6 studies) with gBRCAm advanced ovarian cancer who had received 3 or more prior lines of chemotherapy. Patients received Olaparib capsules 400 mg orally twice daily until disease progression or unacceptable tolerability. The median exposure to Olaparib in these patients was 5.2 months.

Confidential Page 35 of 91

 $\dagger$  Represents grouped terms of related terms that reflect the medical concept of the adverse reaction.

† This number represents the safety population. The derived values in the table are based on the total number of evaluable patients for each laboratory parameter.

‡ Represents the proportion of subjects whose mean corpuscular volume was > ULN.

There were 8 (4%) patients with adverse reactions leading to death, two were attributed to acute leukemia, and one each was attributed to COPD, cerebrovascular accident, intestinal perforation, pulmonary embolism, sepsis, and suture rupture. Adverse reactions led to dose interruption in 40% of patients, dose reduction in 4%, and discontinuation in 7%.

Below tables summarize the adverse reactions and laboratory abnormalities from the pooled studies.

# Table: Adverse Reactions Reported in Pooled Data (≥20% of Patients Who Received Olaparib)

Adverse Reaction	Olaparib capsules n=223		
	Grades 1-4 (%)	Grades 3-4 (%)	
General Disorders	-	2.020	
Fatigue/asthenia	66	8	
Gastrointestinal Disorders		5388	
Nausea	64	3	
Vomiting	43	4	
Diarrhea	31	1	
Dyspepsia	25	0	
Decreased appetite	22	1	
Blood and Lymphatic Disorders		200.00	
Anemia	34	18	
Infections and Infestations			
Nasopharyngitis/URI	26	0	
Musculoskeletal and Connective Tissue Disorder	s		
Arthralgia/musculoskeletal pain	21	0	
Myalgia	22	0	

# Table: Laboratory Abnormalities Reported in ≥25% of Patients in Pooled Data

Laboratory Parameter	Olaparib capsules n † =223		
	Grades 1-4 (%)	Grades 3-4 (%)	
Decrease in hemoglobin	90	15	
Mean corpuscular volume elevation	57	# (E)	
Decrease in lymphocytes	56	17	

Confidential Page 36 of 91

Decrease in platelets	30	3
Increase in creatinine	30	2
Decrease in absolute neutrophil count	25	7

\* Patients were allowed to enter clinical studies with laboratory values of CTCAE Grade 1.

The following adverse reactions and laboratory abnormalities have been identified in ≥10 to <20% of the 223 patients receiving Olaparib and not included in the table: cough (16%), constipation (16%), dysgeusia (16%), headache (15%), peripheral edema (14%), back pain (14%), urinary tract infection (14%), dyspnea (13%), and dizziness (11%).

The following adverse reactions and laboratory abnormalities have been identified in <10% of the 223 patients receiving Olaparib and not included in the table: leukopenia (9%), pyrexia (8%), peripheral neuropathy (5%), hypomagnesemia (5%), rash (5%), stomatitis (4%), MDS/AML (1.8%), and venous thrombosis (including pulmonary embolism) (1%).

## Germline BRCA-mutated HER2-negative Metastatic Breast Cancer

#### OlvmpiAD

The safety of Olaparib was evaluated in gBRCAm patients with HER2-negative metastatic breast cancer who had previously received up to two lines of chemotherapy for the treatment of metastatic disease in OlympiAD. Patients received either Olaparib tablets 300 mg orally twice daily (n=205) or a chemotherapy (capecitabine, eribulin, or vinorelbine) of the healthcare provider's choice (n=91) until disease progression or unacceptable toxicity. The median duration of study treatment was 8.2 months in patients who received Olaparib and 3.4 months in patients who received chemotherapy.

Among patients who received Olaparib, dose interruptions due to an adverse reaction of any grade occurred in 35% and dose reductions due to an adverse reaction occurred in 25%. Discontinuation due to an adverse reaction occurred in 5% of patients receiving Olaparib.

Below tables summarize the adverse reactions and laboratory abnormalities in OlympiAD.

Table: Adverse Reactions\* in OlympiAD (≥20% of Patients Who Received Olaparib)

Adverse Reaction	Olaparib tablets n=205		Chemo n=	2,000
	Grades 1-4 (%)	Grades 3-4 (%)	Grades 1-4 (%)	Grades 3-4 (%)
Gastrointestinal Disorders				

Confidential Page 37 of 91

† This number represents the safety population. The derived values in the table are based on the total number of evaluable patients for each laboratory parameter

58	0	35	1
30	0	15	1
21	1	22	0
-			
40	16	26	4
27	9	50	26
25	5	31	13
n Site Condition	ons		Č CALV
37	4	36	1
	71	-	_
27	1	22	0
16-2-	NEW-IL		
20	1	15	2
	30 21 40 27 25 n Site Condition 37	30 0 21 1 1 40 16 27 9 25 5 m Site Conditions 37 4 27 1	30 0 15 21 1 22  40 16 26 27 9 50 25 5 31  n Site Conditions  37 4 36

\* Graded according to NCI CTCAE v4.0.

In addition, adverse reactions in OlympiAD that occurred in <20% of patients receiving Olaparib were cough (18%), decreased appetite (16%), thrombocytopenia (11%), dysgeusia (9%), lymphopenia (8%), dyspepsia (8%), dizziness (7%), stomatitis (7%), upper abdominal pain (7%), rash (5%), increase in serum creatinine (3%), and dermatitis (1%).

Table: Laboratory Abnormalities Reported in ≥25% of Patients in OlympiAD

	Olaparib tablets n † = 205		Chemotherapy n † = 91	
Laboratory Parameter*	Grades 1-4 (%)	Grades 3-4 (%)	Grades 1-4 (%)	Grades 3-4 (%)
Decrease in hemoglobin	82	17	66	3
Decrease in lymphocytes	. 73	21	63	3
Decrease in leukocytes	71	8	70	23
Increase in mean corpuscular volume ‡	71	(#)	33	
Decrease in absolute neutrophil count	46	11	65	38

Confidential Page 38 of 91

† Represents grouped terms consisting of anemia (anemia crythropenia, hematocrit decreased, hemoglobin decreased and redblood cell count decreased).

‡Represents grouped terms consisting of neutropenia (febrile neutropenia, granulocyte count decreased, granulocytopenia, neutropenia, neutropenia infection, neutropenia sepsis, and neutrophil count decreased).

§ Represents grouped terms consisting of leukopenia (leukopenia and white blood cell count decreased).

I Represents grouped terms consisting of bronchitis, influenza, lower respiratory tract infection, nasopharyngitis, pharyngitis, respiratory tract infection, rhinitis, sinusitis, upper respiratory tract infection, and upper respiratory tract infection bacterial.

Decrease in platelets	33	3	28	0	

- \* Patients were allowed to enter clinical studies with laboratory values of CTCAE Grade 1.
- † This number represents the safety population. The derived values in the table are based on the total number of evaluable patients for each laboratory parameter.
- ‡ Represents the proportion of subjects whose mean corpuscular volume was > ULN.

# Postmarketing Experience

The following adverse reactions have been identified during post approval use of Olaparib. Because these reactions are reported voluntarily from a population of uncertain size, it is not always possible to reliably estimate their frequency or establish a causal relationship to drug exposure.

- Immune System Disorders: Hypersensitivity including angioedema.
- Skin and subcutaneous tissue disorders: Erythema nodosum, rash, dermatitis.

# 5.4 Warnings and precautions

## Myelodysplastic Syndrome/Acute Myeloid Leukemia

Myelodysplastic syndrome (MDS)/Acute Myeloid Leukemia (AML) has occurred in patients treated with Olaparib and some cases were fatal.

In clinical studies enrolling 2901 patients with various cancers who received Olaparib as a single agent, the cumulative incidence of MDS/AML was approximately 1.5% (43/2901). Of these, 51% (22/43) had a fatal outcome. The median duration of therapy with Olaparib in patients who developed MDS/AML was 2 years (range: < 6 months to > 10 years). All of these patients had received previous chemotherapy with platinum agents and/or other DNA damaging agents including radiotherapy.

Do not start Olaparib until patients have recovered from hematological toxicity caused by previous chemotherapy (≤ Grade 1). Monitor complete blood count for cytopenia at baseline and monthly thereafter for clinically significant changes during treatment. For prolonged hematological toxicities, interrupt Olaparib and monitor blood counts weekly until recovery. If the levels have not recovered to Grade 1 or less after 4 weeks, refer the patient to a hematologist for further investigations, including bone marrow analysis and blood sample for cytogenetics. If MDS/AML is confirmed, discontinue Olaparib.

## Pneumonitis

In clinical studies enrolling 2901 patients with various cancers who received Olaparib as a single agent, the incidence of pneumonitis, including fatal cases, was 0.8% (24/2901). If patients present with new or worsening respiratory symptoms such as dyspnea, cough and fever, or a radiological abnormality occurs, interrupt Olaparib treatment and promptly assess the source of the symptoms. If pneumonitis is confirmed,

Confidential Page 39 of 91

discontinue Olaparib treatment and treat the patient appropriately.

## **Embryo-Fetal Toxicity**

Olaparib can cause fetal harm when administered to a pregnant woman based on its mechanism of action and findings in animals. In an animal reproduction study, administration of olaparib to pregnant rats during the period of organogenesis caused teratogenicity and embryo-fetal toxicity at exposures below those in patients receiving the recommended human dose of 300 mg twice daily. Apprise pregnant women of the potential hazard to a fetus and the potential risk for loss of the pregnancy. Advise females of reproductive potential to use effective contraception during treatment and for 6 months following the last dose of Olaparib.

#### Venous Thromboembolic Events

Venous thromboembolic events, including pulmonary embolism, occurred in 7% of patients with metastatic castration resistant prostate cancer who received Olaparib plus androgen deprivation therapy (ADT) compared to 3.1% of patients receiving enzalutamide or abiraterone plus ADT in the PROfound study. Patients receiving Olaparib and ADT had a 6% incidence of pulmonary embolism compared to 0.8% of patients treated with ADT plus either enzalutamide or abiraterone. Monitor patients for signs and symptoms of venous thrombosis and pulmonary embolism and treat as medically appropriate, which may include long-term anticoagulation as clinically indicated.

# 5.5 Indications and usage

# First-Line Maintenance Treatment of BRCA-mutated Advanced Ovarian Cancer

Olaparib is indicated for the maintenance treatment of adult patients with deleterious or suspected deleterious germline or somatic BRCA-mutated advanced epithelial ovarian, fallopian tube or primary peritoneal cancer who are in complete or partial response to first-line platinum-based chemotherapy. Patients must have confirmation of deleterious or suspected deleterious germline and/or somatic mutations in the BRCA 1 or 2 using a validated test.

# Maintenance Treatment of Recurrent Ovarian Cancer

Olaparib is indicated for the maintenance treatment of adult patients with recurrent epithelial ovarian, fallopian tube or primary peritoneal cancer, who are in complete or partial response to platinum-based chemotherapy. There is no requirement for BRCA1/2 testing.

# Advanced Germline BRCA-mutated Ovarian Cancer After 3 or More Lines of Chemotherapy

Olaparib is indicated for the treatment of adult patients with deleterious or suspected deleterious germline BRCA-mutated (gBRCAm) advanced ovarian cancer who have been treated with three or more prior lines of chemotherapy. Patients must have confirmation of a deleterious or suspected deleterious gBRCA1/2 mutation

Confidential Page 40 of 91

before treatment. gBRCA1/2 mutation status should be determined by a validated test.

# Germline BRCA-mutated HER2-negative Metastatic Breast Cancer

Olaparib is indicated for the treatment of adult patients with deleterious or suspected deleterious gBRCAm, HER2-negative metastatic breast cancer, who have been treated with chemotherapy in the neoadjuvant, adjuvant, or metastatic setting. Patients with hormone receptor (HR)-positive breast cancer should have been treated with a prior endocrine therapy or be considered inappropriate for endocrine therapy. Patients must have confirmation of a deleterious or suspected deleterious gBRCA1/2 mutation before treatment. gBRCA1/2 mutation status should be determined by a validated test method.

# 5.6 Therapeutic Dosage

# DOSAGE AND ADMINISTRATION

#### **Patient Selection**

Patients for treatment with Olaparib should be selected based on the presence of deleterious or suspected deleterious BRCA mutations, or genomic instability based on the indication, biomarker, and sample type as indicated in the table below.

Table: Biomarker Testing for Patient Selection for indications included in the study

Indication	Biomarker	Sample Type		
	6. : : : : : : : : : : : : : : : : : : :	Tumor	Blood	
First-line maintenance treatment of germline or somatic BRCAm advanced ovarian cancer	BRCA1m, BRCA2m	х	X	
Maintenance treatment of recurrent ovarian cancer	No requirement for biomarker testing			
Advanced gBRCAm ovarian cancer	gBRCA1m, gBRCA2m		X	
gBRCAm HER2- negative metastatic breast cancer	gBRCA1m, gBRCA2m		x	

Confidential Page 41 of 91

# 5.7 Contraindication

Hypersensitivity to the active substance or to any of the excipients of olaparib. Breast-feeding during treatment and for 1 month after the last dose.

# 5.8 Drug Interaction

## **Use with Anticancer Agents**

Clinical studies of Olaparib with other myelosuppressive anticancer agents, including DNA damaging agents, indicate a potentiation and prolongation of myelosuppressive toxicity.

# Effect of Other Drugs on Olaparib

## Strong and Moderate CYP3A Inhibitors

Coadministration of CYP3A inhibitors can increase olaparib concentrations, which may increase the risk for adverse reactions. Strong and Moderate CYP3A Inhibitors are prohibited during the study (refer annexure IV).

### Strong and Moderate CYP3A Inducers

Concomitant use with a strong or moderate CYP3A inducer decreased olaparib exposure, which may reduce Olaparib efficacy. Strong and Moderate CYP3A Inducers are prohibited during the study (refer annexure IV).

# 5.9 Use in specific populations

### Pregnancy

#### Risk Summary

Based on findings in animals and its mechanism of action, Olaparib can cause fetal harm when administered to a pregnant woman. There are no available data on Olaparib use in pregnant women to inform the drug-associated risk. In an animal reproduction study, the administration of olaparib to pregnant rats during the period of organogenesis caused teratogenicity and embryo-fetal toxicity at exposures below those in patients receiving the recommended human dose of 300 mg twice daily. Apprise pregnant women of the potential hazard to the fetus and the potential risk for loss of the pregnancy.

The estimated background risk of major birth defects and miscarriage for the indicated population is unknown. The estimated background risk in the U.S. general population of major birth defects is 2-4%; and the risk for spontaneous abortion is approximately 15-20% in clinically recognized pregnancies.

#### Females and Males of Reproductive Potential

# **Pregnancy Testing**

Confidential Page 42 of 91

Pregnancy testing for females of reproductive potential is required prior to initiating treatment with Olaparib.

## Contraception

Olaparib can cause fetal harm when administered to a pregnant woman. Advise females of reproductive potential to use effective contraception during treatment with Olaparib and for at least 6 months following the last dosc.

# **Renal Impairment**

No dosage modification is recommended in patients with mild renal impairment (CLcr 51 to 80 mL/min estimated by Cockcroft-Gault). Patients with moderate (CLcr 31 to 50 mL/min) and severe (CLcr ≤30 mL/min) renal impairment are not eligible for the study. Olaparib dosage should be reduced to 200 mg twice daily in patients with moderate renal impairment (CLcr 31 to 50 mL/min). There are no data in patients with severe renal impairment or end-stage disease (CLcr ≤30 mL/min) If dose reduction is needed, the patient should be withdrawn from the study.

# **Hepatic Impairment**

No adjustment to the starting dose is required in patients with mild or moderate hepatic impairment (Child-Pugh classification A and B). There are no data in patients with severe hepatic impairment (Child-Pugh classification C).

## 6.0 OBJECTIVE

- Primary Objective: To assess the pharmacokinetics and establish bioequivalence of the Test Product (Olaparib tablets, 150 mg) relative to that of Reference Product (Lynparza® (olaparib) tablets 150 mg) in patients with BRCA mutated ovarian cancer, recurrent ovarian cancer or metastatic breast cancer.
- Secondary Objective: To monitor the adverse events of patients and to assess safety of each of the two
  formulations.

#### 7.0 STUDY DESIGN

A randomized, open label, multi-centre, two-treatment, two-period, two-sequence, two-stage, multiple dose, steady-state, crossover, bioequivalence study of Olaparib tablets, 150 mg and Lynparza® (olaparib) tablets 150 mg in patients with BRCA mutated ovarian cancer, recurrent ovarian cancer or metastatic breast cancer under fasting condition.

### Rationale:

The sponsor has developed a generic alternative to the reference-listed brand of olaparib 150 mg tablets.

Confidential Page 43 of 91

Therefore, this study is being conducted to evaluate the bioequivalence of the test product Olaparib tablets, 150 mg with Lynparza® (olaparib) tablets 150 mg

in patients with BRCA mutated ovarian cancer, recurrent ovarian cancer or metastatic breast cancer under fasting condition. Current study is randomized, open label, multi-center, two-treatment, two-period, two-sequence, two-stage, multiple dose, steady-state, bioequivalence study. The study design and endpoints are based on the FDA product specific guidance of Olaparib tablet 150 mg.

# Rationale for selection of two-stage design:

Bioequivalence studies are generally conducted in healthy subjects and therefore organized in a way that all study subjects are dosed at the same time. Consequently, all the superseding procedures (blood draws, meals, safety checks, bioanalytics) are done for all subjects in parallel. In contrast, if a bioequivalence study is done in patients, these are being recruited for the study as they come to the doctor's office, meaning that they are included in the study one by one. In such instances it therefore makes sense to have an interim check to assess whether adequate study power was already achieved, and recruitment can be stopped. When the CV is relatively high and not enough data are known, a two-stage adaptive design is ideal since it allows to measure the observed variability from the actual patients participating in the trial and make adjustments as required and as planned in the methodology (approved by the regulators). In addition, adaptive designs are encouraged also due to COVID-19 Pandemic, as indicated by the FDA public note. For these reasons, two-stage design is proposed for this bioequivalence study.

#### 7.1 Number of Patients

Considering a maximum expected intra-patient variability of 35% based on available literature estimates, a true ratio (T/R) of 0.95, 56 evaluable patients are adequate to achieve at least 81% power at 5% level of significance to meet the bioequivalence limit of 80.00% to 125.00% at Stage 1.

Sufficient number of patients will be enrolled to have 56 evaluable patients in the Stage 1 (about, but not limited to, 70 enrolled patients) and Stage 2 sample size (if needed) will be decided on the basis of data (observed CV) obtained after the completion of Stage 1. Maximum sample size (Stage 1 + Stage 2) is expected, but not limited to, approximately 120 enrolled patients. This is a 2-stage design according to Potvin C method. Overall expected power is 86%.

Enrollment will be continued until at least 56 evaluable patients will complete the Stage 1. In case additional patients are recruited, those patients will continue the study until completion/withdrawal and be included in the pharmacokinetic and statistical analyses as applicable.

Note: Patients enrolled in Stage 1 will not be eligible for Stage 2.

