#### **Pharmacokinetics**

The area under the curve (AUC) of olaparib increases approximately proportionally following administration of single doses of 25 mg to 450 mg (0.08 to 1.5 times the recommended dose) and maximal concentrations (Cmax) increased slightly less than proportionally for the same dose range. Olaparib showed time-dependent pharmacokinetics and an AUC mean accumulation ratio of 1.8 is observed at steady state following a dose of 300 mg twice daily.

The mean (CV%) olaparib Cmax is 5.4 μg/mL (32%) and AUC is 39.2 μg\*h/mL (44%) following a single 300 mg dose. The mean steady state olaparib Cmax and AUC is 7.6 μg/mL (35%) and 49.2 μg\*h/mL (44%),

Confidential Page 27 of 91

following a dose of 300 mg twice daily.

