9.2.1 Steps of a two stage design according to Potvin C

Page 20 of 30

Stage 1:

Step1:

Evaluate the power at stage 1 using the variance estimate from stage 1, GMR of 0.95 and an α level of 0.05 for each of C_{maxSS} and AUC_{(0- τ)SS} parameters.

Before proceeding to Step 2, notify the sponsor (via email) regarding stage 1 power and CV values. However, the other BE assessment results (e.g. GMR point estimates or confidence intervals) should not be calculated at Step 1 nor shared with the sponsor. After a confirmatory email is received from the sponsor, proceed to Step 2.

Step 2:

Step 2.1: If power (calculated using the observed variability and GMR of 0.95) is greater than or equal to 80% for both of the parameters (C_{maxSS} and $AUC_{(0-\tau)SS}$), evaluate BE at stage 1 using an α level of 0.05 and stop regardless of whether BE is met or not.

OR

Step 2.2: If the power for either of the two parameters (C_{maxSS} or AUC_{(0- τ)SS}) is less than 80%, evaluate BE using an α level of 0.0294.

Step 2.2.1: If the BE criterion is met, stop.

OR

Step 2.2.2: If the BE criterion is not met, calculate the sample size for stage 2 based on the variance estimated at stage 1, GMR of 0.95 and an α level of 0.0294, round up to nearest even number, add 20% subjects for dropouts and continue to stage 2. If the calculated sample size for stage 2 is less than 12, include at least 12 subjects in stage 2. If the GMR point estimate for any parameter (C_{maxSS} or AUC_{(0-\tau)SS}) is outside 80.00%-125.00% then study will not proceed for stage 2.

Stage 2

Evaluate BE at stage 2 using data pooled from both stages and an α level of 0.0294. Stop here whether BE is met or not and regardless of the power achieved.

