9.2.7 Bioequivalence criteria

For Stage 1 with Power \geq 80%:

Based on the statistical results of 90% confidence intervals for the geometric least squares means ratio for the ln-pharmacokinetic parameters C_{maxSS} and $AUC_{(0-\tau)SS}$ for Olaparib the conclusions will be drawn whether test formulation is bioequivalent to reference formulation under Fasting condition. Acceptance range for bioequivalence is 80.00%-125.00% for 90% confidence intervals of the geometric least squares means ratio of C_{maxSS} and $AUC_{(0-\tau)SS}$.

For Stage 1 with Power < 80% and for Stage 2, if required:

Based on the statistical results of 94.12% confidence intervals for the geometric least squares means ratio for the log-transformed pharmacokinetic parameters C_{maxSS} and $AUC_{(0-\tau)SS}$ for Olaparib the conclusions will be drawn whether test formulation is bioequivalent to reference formulation under Fasting condition. Acceptance range for bioequivalence is 80.00%-125.00% for 94.12% confidence intervals of the geometric least square means ratio of C_{maxSS} and $AUC_{(0-\tau)SS}$.

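### The stated 81% and 86% powers are for one PK parameter; bioequivalence is needed on both, and at the planning inputs (both CVs 35%, both ratios 0.95) overall power is about 76-83%

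*Protocol*

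**What the plan says.** **Planning figures.** Protocol 7.1 starts from one CV, "Considering a maximum expected intra-patient variability of 35% based on available literature estimates", and a true ratio of 0.95. It concludes that "56 evaluable patients are adequate to achieve at least 81% power at 5% level of significance", and that for the two-stage design "Overall expected power is 86" (per cent). SAP 3.1 repeats this. Neither place says whether the figures refer to one parameter or to both.

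**Success criterion.** SAP 9.2.7 (and Protocol 15.2.6) reads "Acceptance range for bioequivalence is 80.00%-125.00% for 90% confidence intervals of the geometric least squares means ratio of" CmaxSS and AUC(0-τ)SS. The same applies to the 94.12% intervals.

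**Adaptive rule, SAP 9.2.1.**
- Alpha 0.05 is used only under this condition: "If power (calculated using the observed variability and GMR of 0.95) is greater than or equal to 80% for both of the parameters". If either parameter falls short, the test is at 0.0294.
- The futility stop begins "If the GMR point estimate for any parameter", so one parameter outside 80.00-125.00% ends the study.
- For stage 2 the instruction is to "calculate the sample size for stage 2 based on the variance estimated at stage 1, GMR of 0.95". It does not say which parameter's variance.

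**Source of the 86%.** It comes from SAP Annexure 13.1 (n1 = 56, CV 35%, maximum total 120). Its tables vary one CV and one true ratio. Section 4 of the annex itself requires the simulation to mirror each step of the real evaluation.

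**CVs by parameter.** The only ones are in Protocol 5.2, in the sentence starting "The mean steady state olaparib Cmax and AUC is": 35% for Cmax and 44% for AUC. It is not said whether these are within or across patients.

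**The concern.** An overall power quoted for a trial with two co-primary parameters will be read as the probability that the trial succeeds. Unless the two parameters are almost perfectly correlated, or one of them is almost certain to pass, the probability of passing on both is lower than the probability of passing on one. The annex's simulation contains neither the second parameter nor the rules that link the two.

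Two things depend on this. The annex uses its power figures to argue that the study is ethically justified. Its cost argument rests on only 9.8% of studies reaching stage 2 and on a 3.9% increase in expected sample size. If both figures describe one parameter, both are too favourable for the trial as it will be judged.

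**Working it through.** **Inputs.** From Protocol 7.1 and SAP 9.2.1: n1 = 56, CV 35%, ratio 0.95, limits 0.80-1.25, alpha 0.05 or 0.0294. From the annex: total capped at 120, and error df reduced for sites, with about n/5 sites. At n = 56 that is 11 sites, so df = 56 - 2 - (11 - 1) = 44; the final df is N - 3 - (sites - 1). The correlation between the two parameters is not in the documents, so 0 to 0.9 is an assumption. Zero is an extreme, since both come from one concentration profile.

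**Step 1: the 81%.** The log-scale error variance is ln(1 + 0.35²) = 0.1156, and the SE of the treatment difference is √(2 × 0.1156/56) = 0.0642. The distance from ln 0.95 to ln 0.80 is 0.1719, or 2.675 SEs. With t(0.95; 54) = 1.674, power is roughly Φ(2.675 - 1.674) = 0.84. The exact two one-sided tests calculation gives 83.5%. Taking 0.35 directly as the log-scale SD gives 81.4%. Both fit the stated figure, for one parameter.

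**Step 2: the 86%.** One-parameter simulation of the annex's design:

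| | Simulated | Annex |
|---|---|---|
| Final power | 86.1% | 86.0% |
| Pass at stage 1 | 80.2% | 80.4% |
| Enter stage 2 | 9.9% | 9.8% |
| Mean total N | 58.2 | 3.9% above 56, i.e. 58.2 |

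So 86% is a one-parameter power.

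**Step 3: both parameters.** The same simulation was run with two correlated parameters under SAP 9.2.1. Alpha 0.05 applies only if both powers reach 80%; otherwise both are tested at 0.0294. The trial stops if either GMR is outside 0.80-1.25, and success needs both to pass. Stage 2 is sized on the larger variance, which is an assumption because the SAP is silent. Each setting used 200,000-400,000 trials, so the Monte Carlo SE is about 0.1 point. Both CVs are 35% and both ratios 0.95:

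| Correlation | One look, n = 56, alpha 0.05 | Overall power | Enter stage 2 |
|---|---|---|---|
| 0 | 69.8% | 76.1% | 24.8% |
| 0.5 | 73.4% | 78.8% | 21.1% |
| 0.7 | 75.6% | 80.3% | 18.5% |
| 0.9 | 79.0% | 82.8% | 14.8% |

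The one-look column uses df 54, to match Step 1. Its first entry can be checked by hand: 0.835² = 0.698. Mean total N is 61.7 at correlation 0 and 59.4 at 0.9, which is 10% and 6% above 56. At correlation 0.99 overall power is 85%, still below 86%.

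**Step 4: how far this depends on the assumptions.**
- *Stage 2 rule.* With no cap and a stage 2 minimum of 12: 76.2%, 78.7%, 80.3%, 82.7%. With stage 2 sized on one fixed parameter: 72.2%, 75.9%, 78.3%, 81.8%.
- *Lower CVs, correlation 0 to 0.9.* CVs 35%/30%: 80-85%. CVs 35%/28%: 82-86%. CVs 35%/25%: 84-86%. CVs 30%/30%: 85-90%.
- *Common CV at which joint power reaches 86%.* About 29.5%, 30%, 31% and 32% at correlation 0, 0.5, 0.7 and 0.9.
- *Second true ratio 1.00.* 83-85% (CVs 35%/35%) and 85-86% (35%/30%).
- *CVs from Protocol 5.2.* Suppose 35% and 44% are across patients, and 65% or 50% of the log variance is within patients (assumption). The CVs are then 28%/35% or 24%/30%, and joint power is 82-86% or 90-91%.

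**Step 5: type I error.** With one true ratio at 1.25 and the other at 1.00 (CVs 35%/35%, 35%/10% and 25%/40%; correlation 0 and 0.9), the rate of false acceptance is 0.015-0.048.

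**The case against.** The strongest reply is that nothing stated is miscalculated: the annex openly runs one CV and one ratio, and its figures reproduce. The 35% is a maximum, so it may describe the more variable parameter only, and no passage says both parameters have it. Correlation 0 is unrealistic; over 0.5-0.9 the range is 79-83%. More than 56 evaluable patients may be available at stage 1. The SAP also re-checks power for each parameter from observed variances, so the planning figure drives no analysis decision.

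Much of this stands. The documents cannot settle whether the trial will in fact fall short of 86%, because they give no within-patient CV per parameter and no correlation. Plausible lower CVs bring joint power to 86% or above.

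It does not rescue the statement as written. The 81% and 86% are themselves quoted at CV 35% and ratio 0.95, so the like-for-like comparison is at those inputs, and there joint power is below 86% even at correlation 0.99. Extra stage 1 patients narrow the gap but do not close it: with n1 = 60 joint power is 77-84%, and with n1 = 62 it is 78-85%. If per-parameter power was intended, the text should say so.

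**Conclusion.** The concern holds. The stated powers are correct for a single parameter but are presented as the power of a trial that must pass on two. With both CVs at 35%, both true ratios at 0.95, n1 = 56 and stage 2 sized on the larger variance, overall power is 76-83% for correlations 0 to 0.9, against 86%. Stage 2 is entered in 15-25% of trials, against 9.8%.

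The calculation is firm given those inputs. Whether they describe olaparib is not known from the documents. The consequence is an overstated planning figure and an understated chance of a second stage, with no risk of a false bioequivalence claim. The unnamed variance for stage 2 sizing is a genuine gap in the rule: sizing on one fixed parameter lowers the range to 72-82%.

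**What to change.** 1. In Protocol 7.1, SAP 3.1 and Annexure 13.1, restate 81% and 86% as power per parameter at CV 35% and ratio 0.95.
2. Beside them, report joint power and the probability of entering stage 2 from a two-parameter simulation of SAP 9.2.1. Cover stated ranges of both CVs and of the correlation, marked as assumptions, and include CVs below 35%.
3. In SAP 9.2.1, Step 2.2.2, name the parameter whose variance sets the stage 2 size (for example, the larger of the two), and simulate that rule.

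Sample size and decision rules stay as they are. The cost is a modest extension of the existing simulation code, and a less favourable stated figure for the case where both CVs are at the maximum.
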